8.2.6 Manufacturer of Investigational Medicinal Product

All SAEs and other reportable events will be reported by the trials office to the manufacturer of the Investigational Medicinal Product (Pfizer) within 24 hours by fax and or email as per the Pfizer Safety Reporting Reference Manual.

9. DATA HANDLING AND RECORD KEEPING

9.1 Data Collection

The Case Report Form (CRF) will comprise a set of forms capturing details of eligibility, baseline characteristics, treatment and outcome details.

This trial will use an electronic data capture (EDC) system which will be used for completion of CRFs. Access to the EDC system will be granted to individuals via the Trial Office. SAE reporting and Notification of Pregnancy will be paper-based.

The CRF must be completed by the Investigator or an authorised member of the site research team (as delegated on the Site Signature and Delegation Log) within the timeframe (found in the eCRF completion guidelines). The exceptions to this are the eligibility Form, SAE Form and Withdrawal Form which must be co-signed by the Investigator and reported in an expedited manner.

Data reported on each form should be consistent with the source data or the discrepancies should be explained. If information is not known, this must be clearly indicated on the form. Missing and ambiguous data will be queried in line with the data validation plan and data management guidelines for the trial. All sections are to be completed before submitting.

In all cases it remains the responsibility of the Investigator to ensure that the CRF has been completed correctly and that the data are accurate.

Trial forms may be amended by the Trials Office, as appropriate, throughout the duration of the trial. Whilst this will not constitute a protocol amendment, new versions of the form will be implemented by participating sites via the EDC system.

9.2 Archiving

It is the responsibility of the Principal Investigator to ensure all essential trial documentation and source records (e.g. signed Informed Consent Forms, Investigator Site Files, Pharmacy Files, patients' hospital notes, copies of CRFs etc) at their site are securely retained for at least 25 years after the end of the trial or following the processing of all biological material collected for research, whichever is the later. Do not destroy any documents without prior approval from the CRCTU Document Storage Manager.

10. QUALITY MANAGEMENT

10.1 Site Set-up and Initiation

All sites will be required to sign a Clinical Study Site Agreement prior to participation. In addition all participating Investigators will be asked to sign the necessary agreements registration forms and supply a current CV and conformation of GCP training to the Trials Office. All members of the site research team will also be required to sign the Site Signature and Delegation Log, which should be returned to the Trials Office. Prior to commencing recruitment all sites will undergo a process of initiation. Key members of the site research team will be required to attend either a meeting or a teleconference covering aspects of the trial design, protocol procedures, Adverse Event reporting, collection and reporting of data and record keeping. Sites will be provided with an Investigator Site File and a Pharmacy File containing essential documentation, instructions, and other documentation required for the conduct of the trial. The Trials Office must be informed immediately of any change in the site research team.

10.2 On-site Monitoring

Monitoring will be carried out as required following a risk assessment and as documented in the AVAIL-T Quality Management Plan. Additional on-site monitoring visits may be triggered for example by poor CRF return, poor data quality, low SAE reporting rates, excessive number of patient withdrawals or deviations. If a monitoring visit is required the Trials Office will contact the site to

arrange a date for the proposed visit and will provide the site with written confirmation. Investigators will allow the AVAIL-T trial staff access to source documents as requested.

10.3 Central Monitoring

Where a patient has given explicit consent sites are requested to send in copies of signed ICF for in-house review.

Trials staff will be in regular contact with the site research team to check on progress and address any queries that they may have. Trials staff will check incoming CRFs via the EDC for compliance with the protocol, data consistency, missing data and timing. Sites will be sent DCFs requesting missing data or clarification of inconsistencies or discrepancies.

Sites may be suspended from further recruitment in the event of serious and persistent non-compliance with the protocol and/or GCP, and/or poor recruitment. Any major problems identified during monitoring may be reported to Trial Management Group (TMG), Trial Safety Committee (TSC) and the relevant regulatory bodies. This includes reporting serious breaches of GCP and/or the trial protocol to the main REC and the MHRA.

10.4 Audit and Inspection

The Investigator will permit trial-related monitoring, audits, ethical review, and regulatory inspection(s) at their site, providing direct access to source data/documents.

Sites are also requested to notify the Trials Office of any MHRA inspections.

10.5 Notification of Serious Breaches

In accordance with Regulation 29A of the Medicines for Human Use (Clinical Trials) Regulations 2004 and its amendments the Sponsor of the trial is responsible for notifying the licensing authority in writing of any serious breach of:

- The conditions and principles of GCP in connection with that trial or;
- The protocol relating to that trial, within 7 days of becoming aware of that breach

For the purposes of this regulation, a “serious breach” is a breach which is likely to effect to a significant degree:

- The safety or physical or mental integrity of the patients of the trial; or
- The scientific value of the trial

Sites are therefore requested to notify the Trials Office of a suspected trial-related serious breach of GCP and/or the trial protocol. Where the Trials Office is investigating whether or not a serious breach has occurred sites are also requested to cooperate with the Trials Office in providing sufficient information to report the breach to the MHRA where required and in undertaking any corrective and/or preventive action.

11. END OF TRIAL DEFINITION

The end of trial will be last patient last visit. The Trials Office will notify the MHRA and main REC that the trial has ended and will provide them with a summary of the clinical trial report within 12 months of the end of trial.

12. STATISTICAL CONSIDERATIONS

12.1 Definition of Outcome Measures

12.1.1 Primary outcome measures

- Best overall response (CR + PR) during the first 8 cycles of treatment will be assessed using contrast-enhanced CT scans of the neck, chest, abdomen and pelvis, using the Revised Response Criteria for Malignant Lymphoma (²⁷)

12.1.2 Secondary outcome measures

- Toxicity assessed using CTCAE v4.0 will be defined as the number and proportion of patients who experience one or more grade 3 or 4 adverse event or serious adverse event of any grade
- Best overall response (Partial Remission (PR) + Complete Response (CR)) at any time of treatment will be assessed using contrast-enhanced CT scans of the neck, chest, abdomen and pelvis, using the Revised Response Criteria for Malignant Lymphoma (²⁷)
- Maximum percentage change in the sum of the product of diameters (SPD) of target tumour masses assessed by contrast-enhanced CT scans of the neck, chest, abdomen and pelvis, using the Revised Response Criteria for Malignant Lymphoma²⁷
- Duration of response is defined as the time from first documented response until relapse/progression, as determined by the Revised Response Criteria²⁷, or death. Patients who are relapse/progression free and alive will be censored at date last seen.
- Progression free survival is defined as the time from date of registration to the date of disease progression or date of death from any cause. Patients not reaching progression or death at the time of analysis will be censored at the last date they were known to be alive and progression free. Patients will be followed up for a minimum of 12 months.
- Overall survival time is defined as the time from date of registration to the date of death from any cause. Patients discontinuing the study, lost to follow-up or still alive at the end of the study will be censored at the date of last follow-up. Patients will be followed up for a minimum of 12 months.

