7.3.5 Radiological Assessment – CT scans

A contrast enhanced CT scan of the neck, chest, abdomen and pelvis will be performed at cycles 3, 6 and 8 of treatment to assess response during treatment. If the patient discontinues treatment early an End of treatment scan should be performed, if a scan has not been conducted with the last 28 days. Scans should be reported with two dimensional measurements of each lesion in millimetres (mm) if measureable.

Immunotherapeutic agents such as avelumab may produce antitumor effects by potentiating endogenous cancer-specific immune responses. The response patterns seen with such an approach may extend beyond the typical time course of responses seen with cytotoxic agents, and can manifest as a clinical response after an initial increase (pseudo-progression) in disease burden. The Investigator's judgment of radiological response on early CT scans should be based on the overall benefit-risk assessment and the patient's clinical condition, including performance status, clinical symptoms, adverse events and laboratory data.

If the patient has not progressed after 8 cycles they will continue to be followed up with CT scans at 12, 16 and 20 months from treatment start or sooner if the investigator is concerned there may be disease progression. After 20 months from treatment start radiological follow-up will be as per local standard with data collected every 6 months.

Response will be assessed according to the Revised Response Criteria for malignant lymphoma²⁷ (appendix 1).

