7.9 Patient Follow Up

All patients will need to be followed up for safety (AEs) up to 30 days (+/- 5 days) after the last dose of avelumab and for disease progression / survival until the end of the trial (minimum of 12 months follow-up from the date of commencing treatment for the last patient).

If the patient stops trial treatment but has not progressed, they will be reviewed with a CT scan of neck, chest, abdomen and pelvis at 8, 12, 16 and 20 months or on clinical suspicion of progression (whichever is sooner).

If there is no evidence of progression after 20 months, patients will have no specific trial follow up, but their referring physician may be contacted every 6 months to determine progression and survival data.

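### Duration of response is censored at the last-seen date but PFS at the last date known progression free; read literally, this can lengthen response for a responder seen without a disease assessment

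*Combined protocol and SAP*

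**What the plan says.** Section 12.1.2 lists three time-to-event outcomes, each with its own censoring wording.

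- **Duration of response:** "Duration of response is defined as the time from first documented response until relapse/progression, as determined by the Revised Response Criteria", or death. The rule for those without an event is "Patients who are relapse/progression free and alive will be censored at date last seen".
- **PFS:** patients without an event "will be censored at the last date they were known to be alive and progression free".
- **OS:** patients who are "lost to follow-up or still alive at the end of the study will be censored at the date of last follow-up".

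Section 12.2 estimates the time-to-event outcomes by Kaplan-Meier, with point estimates at 6 and 12 months.

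Disease status is established as follows. Under Section 7.3.5, CT scans "will be performed at cycles 3, 6 and 8 of treatment to assess response during treatment". For patients who have not progressed by then, "they will continue to be followed up with CT scans at 12, 16 and 20 months from treatment start". After that, "After 20 months from treatment start radiological follow-up will be as per local standard with data collected every 6 months"; Section 7.9 adds that "their referring physician may be contacted every 6 months to determine progression and survival data". Table 2 and Section 7.3.4 place the clinical disease assessment on day 1 of each cycle and at the End of Treatment visit, and Table 2 repeats it at the 12, 16 and 20 month visits. It is not scheduled on day 15, when patients attend for bloods and infusion. Section 7.2 allows treatment beyond cycle 8.

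**The concern.** Being seen alive is not the same as being assessed for progression. The event for duration of response is progression by lymphoma response criteria, which turn mainly on measured lesions. If the last-seen date is programmed as any last contact, time after the last assessment counts as continued response. The PFS rule in the neighbouring bullet is tied to known progression-free status and need not credit that time.

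Two things are at stake. The same patient can carry inconsistent dates in two related outcomes, and the duration of response curve can sit higher than it would under the PFS rule. Responders will be few, so each censoring date carries weight. The choice between readings would also be left to whoever programs the analysis.

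**Working it through.** **No plan figure to reproduce.** The documents state no design figure for duration of response or PFS. The plan's only calculation concerns the response rate: with a Beta(1,1) prior (an assumption, since the parameters are not given), 11/30 and 13/30 responses give 60.3% and 84.1%, matching the stated 60% and 84%. Nothing here changes those figures.

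**Gaps between scans.** Take each on-treatment scan at the end of its 28-day cycle and a month as 30.44 days.
- Cycle 3: 84/30.44 = 2.76 months. Cycle 6: 168/30.44 = 5.52. Cycle 8: 224/30.44 = 7.36.
- Gaps: 2.76, 1.84, 12 − 7.36 = 4.64, 4.0 and 4.0 months.

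**Gaps if clinical disease assessments also count.**
- On treatment, a day 15 visit is 14 days after the day 1 assessment: 14/30.44 = 0.46 month.
- Off treatment after 8 cycles, the End of Treatment visit falls at about (210 + 28)/30.44 = 7.82 months, so the gap to month 12 is 4.18 months; later gaps are 4.0.

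The upper figure of about 4 to 4.6 months therefore applies when status is dated from scans, or when an off-treatment patient is seen informally between visits. For a patient on continued treatment it falls to about two weeks if the day 1 assessment is accepted.

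**Same patient, two dates.** Assume last scan at month 12, last seen without disease assessment at month 15, registration close to treatment start, and PFS censored at the scan. PFS is 12.0 months. Duration of response is:
- first response at cycle 3: 15 − 2.76 = 12.24 months;
- at cycle 6: 15 − 5.52 = 9.48 months;
- at cycle 8: 15 − 7.36 = 7.64 months.

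In each case the two outcomes are censored on calendar dates 3 months apart.

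**Direction.** Each Kaplan-Meier factor is 1 − d/n, with d events among n at risk. Later censoring leaves d and the event times alone and can only raise n. With 8 rather than 6 at risk at one event, the factor is 7/8 = 0.875 rather than 5/6 = 0.833. So the curve under the last-seen rule is never lower.

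**Size, by simulation on assumed inputs.** The documents give no duration of response assumptions. The inputs were 11 responders (the sample size section's first scenario); median duration 4, 6 or 12 months; median time to loss to follow-up 12 months; first response at cycle 3, 6 or 8 in 60/25/15%. In the first row none or half of progressions were found between scans; in the other rows, half. The same patients were censored at the last-seen date and at the last scan. The rise from using the last-seen date was:

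| Scenario | At 6 months | At 12 months | Mean extra time per censored responder |
|---|---|---|---|
| Scans on schedule | 1–3 points | 3–4 points | 1.6–1.9 months |
| 20% seen but no longer scanned | 4–7 points | 8–10 points | 3.1–3.3 months |
| 40% seen but no longer scanned | 6–11 points | 13–15 points | 4.3–4.5 months |

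When every response began at the cycle 3 scan and every progression fell on a scheduled scan, the rise was zero. The comparator is the last scan. Accepting clinical assessments as well moves its censoring dates later, so within each scenario these figures are upper bounds for the change proposed under the fix.

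**After month 20.** The latest first response within 8 cycles is at about 7.4 months, and 7.4 + 12 = 19.4 months. A responder scanned at month 20 is already past the 12-month estimate under either rule.

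**The case against.** The strongest reply is that the conflict depends on how both phrases are read. The duration of response sentence covers only patients who are free of progression, and the PFS sentence names no scan. A clinical review at month 15 without progression could censor both outcomes at month 15. This stands in part: the documents do not force the two dates apart. Nor do they require the last-seen date to carry an assessment, and different wording in adjacent bullets invites different programming.

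A reader might infer more than the documents support:

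- **That progression could not be observed between scans.** It can. Sections 7.3.5 and 7.9 and the footnotes to Table 2 provide for CT on suspicion of progression, treated patients have a clinical disease assessment on day 1 of each cycle, and deaths count as events.
- **That all follow-up is affected.** The 12, 16 and 20 month visits pair clinical assessment with CT, so for an off-treatment patient on schedule the last visit is a scan visit.
- **That response will outlast PFS.** In the example this happens only for a cycle 3 responder, by 0.24 month, and not for later responders.
- **That six-monthly data after month 20 inflate the planned estimates.** For responses within 8 cycles they do not.

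The size is also modest against sampling error: with 11 patients and a proportion near 50%, a 95% interval is roughly ±1.96 × √(0.25/11) = ±30 points. The larger simulated shifts need 20–40% of responders to be seen but not scanned, which the documents give no reason to expect.

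Finally, censoring strictly at the last scan while counting events found between scans could bias the curve downward. In the settings with half of progressions found between scans and scans on schedule, it did not: the 12-month last-scan estimates were 14.0%, 25.8% and 50.1% against true values of 12.5%, 25% and 50%. A larger off-schedule share could change that, which is a reason to accept protocol clinical assessments as well as CT.

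**Conclusion.** The point holds as an inconsistency between two stated censoring rules. If the last-seen date is applied literally, a responder seen without a disease assessment stays at risk beyond the date progression-free status was last established. Kaplan-Meier duration of response can then be higher, never lower, than under the PFS rule. The documents do not support saying that it is biased, only that it can be under that reading.

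The extra time is at most about 4 to 4.6 months per censored responder between scheduled scans, much less for a treated patient whose day 1 assessment is accepted, and near zero when the last contact is a scan visit. The percentage-point shifts rest wholly on assumed inputs. The outcome is secondary; the response rate, its posterior probabilities and the interim rule are untouched. This is a cheap improvement, not a flaw in the design.

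**What to change.** Use one censoring rule, identically worded, for duration of response and PFS. A patient without relapse, progression or death is censored at the date of the last disease assessment (CT or protocol clinical disease assessment) that showed no relapse or progression. This replaces the last-seen date for duration of response. Copying the present PFS wording across would remove the disagreement but leave open what counts as known progression free, so the rule should name the qualifying assessments. OS can stay as it is.

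The cost is a sentence and a short definition, agreed before the analysis, using dates already collected. Duration of response, and possibly PFS, may be slightly shorter.

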7.10 Patient Withdrawal of Consent

In the event of a patient's decision to withdraw from the trial, the Investigator should ascertain from which aspects of the trial the patient wishes to withdraw and record the details on the appropriate CRF. All information and blood/tissue samples collected up until point of retraction will be retained and analysed. If a patient chooses to withdraw from treatment only, the patient should discontinue treatment and continue to be assessed in accordance with the protocol. If a patient wishes to withdraw from the trial (i.e. including trial specific assessments), but is willing for further data to be supplied to the Trials Office, then further routine "follow-up" data (e.g. disease status and survival) will continue to be supplied by the Investigator to the Trials Office.

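### The overall survival censoring rule in 12.1.2 names patients who discontinue the study without limiting it to those not known to have died, so read literally it can censor a recorded death

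*Combined protocol and SAP*

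**What the plan says.** Section 12.1.2 defines the OS event without restriction: "Overall survival time is defined as the time from date of registration to the date of death from any cause". The censoring rule follows: "Patients discontinuing the study, lost to follow-up or still alive at the end of the study will be censored" at last follow-up. Of its three groups, only the last is described by vital status.

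The PFS rule in the same list depends on the event: "Patients not reaching progression or death at the time of analysis will be censored at the last date they were known to be alive" and free of progression. Duration of response likewise censors only patients who are alive without relapse or progression.

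Three sections govern follow-up:

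- Section 7.8 keeps all patients in protocol follow-up after treatment stops, unless they withdraw specific consent.
- Section 7.9 follows patients for progression and survival to the end of the trial.
- Section 7.10 keeps patients who withdraw from treatment only under assessment. For a patient who withdraws from trial assessments "but is willing for further data to be supplied to the Trials Office", routine "data (e.g. disease status and survival) will continue to be supplied by the Investigator to the Trials Office".

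Section 12.2 reports time-to-event outcomes by Kaplan-Meier, with estimates and 95% confidence intervals at 6 and 12 months.

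**The concern.** The OS rule makes leaving the study a reason to censor in itself, while the follow-up sections arrange for deaths to be reported after a patient has left. An analyst who follows 12.1.2 to the letter would discard deaths that the trial took care to collect.

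Two things are at stake. The first is coherence: a patient with no earlier progression could have a PFS event that consists of a death, and no OS event. The second is the estimate. Kaplan-Meier assumes that censored patients have the same later risk as those who remain. If leaving is related to prognosis, the 6- and 12-month OS figures shift, and the confidence interval does not show it.

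**Working it through.** **1. Who is affected.** Stopping treatment alone is not discontinuing the study, because 7.8 and 7.10 keep those patients in follow-up. Patients who refuse further data must be censored under any rule. That leaves patients who withdraw from trial assessments but allow further data. Patients removed from the study under the QTc rule in 7.3.3 may belong here too; the text does not say.

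**2. One patient traced.** Suppose such a patient leaves at time u without progression and dies at a later time v, reported under 7.10. The PFS rule gives an event at v. The OS rule read literally gives a censored time, at u or at v depending on what last follow-up means, but no event either way. If progression came before death, the PFS event is the progression and the two outcomes do not conflict, although the death is still lost from OS.

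**3. The plan's own figures.** The plan states no OS figure to reproduce. Its design figures concern response only. With a flat Beta(1,1) prior, 11/30 responses give a Beta(12,20) posterior and P(rate > 35%) = 60.3% (stated 60%); 13/30 give Beta(14,18) and 84.1% (stated 84%). Neither depends on OS censoring.

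**4. Illustrative size.** From the documents: median OS 6.0 months after relapse in initial responders (1.2.3), and reporting at 6 and 12 months (12.2). Assumed, because the documents give nothing: exponential survival; 20% of patients marked to leave at a time uniform over months 0 to 6 if still alive; all of them allow further data; hazard after leaving is h times the hazard before.

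- Hazard: λ = ln 2 / 6 = 0.1155 per month.
- Share who actually leave before death: 0.20 × (1 − 0.5)/ln 2 = 14.4%, about 4.3 of 30 patients.
- Literal rule: leavers have the common hazard until they leave, so Kaplan-Meier estimates exp(−λt), which is 50% at 6 months and 25% at 12.
- Counting every known death: S(t) = 0.80 exp(−λt) + 0.20 M(t), where M(t) = 2^(−ht/6) × (2^(h−1) − 1)/((h − 1) ln 2). At h = 1, M(t) = exp(−λt).

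| h | M(6) | S(6) | Literal minus S(6) | M(12) | S(12) | Literal minus S(12) |
|---|---|---|---|---|---|---|
| 0.5 | 0.598 | 52.0% | −2.0 | 0.423 | 28.5% | −3.5 |
| 1 | 0.500 | 50.0% | 0 | 0.250 | 25.0% | 0 |
| 2 | 0.361 | 47.2% | +2.8 | 0.090 | 21.8% | +3.2 |
| 4 | 0.210 | 44.2% | +5.8 | 0.013 | 20.3% | +4.7 |

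A simulation of 400,000 survival times per scenario agrees with this table to about 0.1 point. Over medians of 2.5, 6 and 18 months (the extremes quoted in 1.2.1 and 1.2.3) and 10% to 30% marked to leave, the difference at 6 or 12 months was 0 at h = 1, +0.3 to +5.5 points at h = 2, +0.4 to +12.1 at h = 4, and −0.5 to −5.2 at h = 0.5.

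**5. Scale.** With 30 patients the 95% half-width is about 1.96 × √(0.5 × 0.5/30) = 18 points at 50% survival and 1.96 × √(0.25 × 0.75/30) = 15 points at 25%. Per patient, Kaplan-Meier passes a censored patient's weight of 1/30 to those still at risk. Censoring instead of counting one death before month 6 therefore raises the 6-month estimate by about (1/30) × S(6)/S(u). With S(6) = 50% that is 1.7 points for an exit near month 0 and 3.3 points near month 6.

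**The case against.** The strongest reply is that the sentence is loose, not wrong. OS has just been defined by death from any cause, so the next sentence can be read as saying where patients without that event are censored. Nobody would take the words on loss to follow-up to discard a known death. Section 7.10 also describes the data supplied after withdrawal as follow-up, so a patient whose survival is still reported is arguably still in follow-up. This reading is available and would make 12.1.2 agree with 7.9 and 7.10. But the text does not state it, and the two neighbouring rules show how it could have been stated. An analyst should not have to choose between readings once the data are known.

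A reader might go further and infer that every patient who discontinues has a death removed from OS, or that OS in this trial is biased upward. The documents support neither. Survival after withdrawal from assessments is supplied only if the patient agrees, and treatment-only withdrawals stay in follow-up. That patients leave mainly when deteriorating is plausible in this disease, but no section says so. A scenario that censors leavers a month or two before death produces an upward bias by construction and does not establish the direction.

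It also stands that OS is a descriptive secondary outcome in a single-arm trial, and that most plausible shifts lie well inside the confidence interval. This limits the importance of the point but does not remove it: the interval describes sampling error, not a rule that omits recorded deaths.

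**Conclusion.** The OS censoring rule is wrong as written, and the matter is minor. It names study discontinuation as a reason to censor without excluding patients known to have died. It differs in this from the PFS and duration-of-response rules, and it sits badly with the survival collection in 7.9 and 7.10. Read literally, it can censor a known death that counts as a PFS event when no progression came first.

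The effect on Kaplan-Meier OS has no fixed sign: it depends on whether leavers do worse, the same or better than those who stay. The size cannot be derived from the documents, which give neither a discontinuation rate nor the later risk of leavers. The few points in the table are illustrations under stated assumptions, and they shrink if some leavers refuse further data. The affected group is probably small. The primary outcome, the sample size and the response-based futility guidance do not depend on this rule.

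**What to change.** Replace the OS censoring sentence in 12.1.2 with:

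*Patients not known to have died will be censored at the date last known alive; every known death counts as an event whatever the patient's treatment or study status, including deaths reported as routine follow-up data under 7.10.*

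Patients who refuse further data are still censored at the date last known alive, so nothing changes for them. OS and PFS then use the same deaths. The change should be made before the final analysis, so that the choice of reading cannot depend on the results.

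The cost is one sentence. No new data are needed, because 7.9 and 7.10 already provide for their collection. The downside for the sponsor is that OS may look slightly less favourable if leavers do worse.
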